# Inclusion Criteria:

- Physician referral
- Persistent symptomatic urogenital MG infection documented by any NAAT 14-90 days after completion of the prior antimicrobial regimen for MG
- Low risk of reinfection defined as no unprotected sex with an untreated sex partner since completion of the prior antimicrobial regimen
- Male or female sex at birth
- ≥18 years of age
- English-speaking
- Able to provide written informed consent
- Able to undergo a test to confirm MG infection at baseline and tests of cure 21-28 days and 42-47 days after completing lefamulin

- Referring physician willing and able to provide needed patient information
- Living in the US

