## Tests of cure

Tests of cure will be performed in the UW Global Health STI Laboratory (laboratory director [name]). The Hologic Aptima MG assay, which we propose to use for tests of cure, has higher sensitivity and specificity than most other assays. Thus, test-of-cure windows when using this assay are generally longer (21-28 days) than when other assays are used. Furthermore, instances of MG recrudescing after an initial negative test subsequent to treatment have been reported, suggesting that additional follow-up after an initial test of cure is warranted in studies of novel antimicrobials. Therefore, we will perform two tests of cure (one at 21-28 days and one at 42-47 days after completion of lefamulin).

The research coordinator will ship Aptima test kits to enrolled patients, one 21-48 days, and one 42-47 days after completion of Lefamulin. In addition to the Aptima collection kit and instructions and shipping materials to return the Aptima tubes to the UW Global Health STI Laboratory, that package will also include materials and instructions for culture specimen collection as described above. Culture specimens will be shipped at the same time as the test of cure specimens.

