## Clinical, symptom, adherence, and side effects data

In addition to the CDC MG Treatment Failure CRF, the study physician will ask about other aspects of the patient medical history and enter this information into a separate UW ITHS REDCap form (concomitant medications, other relevant medical history, etc.). Where available, the study physician will also obtain Gram stain results and chemistry panel with liver function test results.

We will also program electronic surveys, using the UW ITHS REDCap platform, that will be completed by the patient on the start date of the first antibiotic course, upon completion of the antibiotic regimen (lefamulin alone or lefamulin and doxycycline), and at the 21-28-day and the 42-47-day test-of-cure timepoints. The REDCap surveys will collect information on dates of

antibiotic use, symptoms, antibiotic adherence, sexual behavior, and side effects. We will also program electronic reminders to remind the patient to complete the REDCap surveys and to mail in the test of cure and culture specimens.

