## **Outcomes**

We will assess one primary outcome and five secondary outcomes.

- Primary Outcome
  - Microbiologic cure defined as a negative Aptima MG test 21-28 days after completing lefamulin
- Secondary Outcomes
  - Microbiologic cure, as defined above, after lefamulin alone compared to microbiologic cure after sequential treatment with doxycycline followed by lefamulin
  - Clinical cure defined as absence of symptoms, absence of visible discharge, and absence of other clinical signs (<5PMNs/hpf on Gram stained smear where available) 21-28 days after completion of the lefamulin
  - Reported adherence to lefamulin (defined by self-reported number of tablets taken)
  - Reported adverse events (defined by self-reported adverse events)
  - Sustained microbiologic cure defined as a negative Aptima MG test 42-47 days after completing lefamulin

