# Sample size

We initially estimated the sample size needed based on the precision around efficacy estimates for lefamulin in a single arm study and estimated that a total of 30 patients with complete data on tests of cure, adherence, and adverse events would provide precision to estimate efficacy  $\geq$ 90% with binomial exact 95% Cl's ranging from 73.5% - 99.9%. Assuming loss to follow-up of up to 30%, **a total of 40 patients will need to be enrolled**.

Because there are fewer people in each arm of a two-arm randomized pilot trial, the statistical power and precision will be somewhat than that estimated for a single arm study. Table 2 compares precision for an arm with 20 randomized persons to one with 30 randomized persons. Even in the case where an arm has only 20 randomized persons, the lower bound of the confidence intervals is >60%, which would still demonstrate benefit.

**Table 2**: Precision around estimated cure rates assuming 40 patients are enrolled and outcome data are available on either 20 participants randomized per arm (if neither regimen meets criteria for futility), or 30 participants randomized to an arm (if one of the regimens meets criteria for futility)

Lefamulin	N=20		N=30	
failures (n)	Estimated cure	95% confidence	Estimated cure	95% confidence
		intervals		intervals
3	85%	62.11 – 96.79	90%	73.5 – 97.9
2	90%	68.30 - 98.77	93%	77.9 – 99.2
1	95%	75.13 – 99.87	96%	82.8 - 99.9

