# Data analysis

We will calculate and present simple proportions and 95% CIs for each of our outcomes. We will not require complete data on all outcomes to be included in analyses. Instead, the denominator will be the total number of patients for whom we have complete outcome data for the outcome of interest. For example, patients with test of cure data but without clinical cure data will be included in the calculation of microbiologic cure but excluded from the calculation of clinical cure.

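### Sustained microbiologic cure is scored on the 42-47 day test alone, so a patient still positive at 21-28 days can count as a sustained cure or drop out of the denominator

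*Combined protocol and SAP*

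**What the plan says.** All references are to the combined protocol and SAP.

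- **Outcomes, primary:** "Microbiologic cure defined as a negative Aptima MG test" 21-28 days after completing lefamulin.
- **Outcomes, secondary:** "Sustained microbiologic cure defined as a negative Aptima MG test" 42-47 days after completing lefamulin. The 21-28 day result is not mentioned.
- **Tests of cure:** the second test is justified because "instances of MG recrudescing after an initial negative test subsequent to treatment have been reported". Both tests are planned for enrolled patients generally, not only for those negative at the first.
- **Data analysis:** each outcome is reported as a proportion with a 95% CI, and "the denominator will be the total number of patients for whom we have complete outcome data for the outcome of interest".
- **Sample size:** "Assuming loss to follow-up of up to 30" per cent.

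No section says how a patient positive at 21-28 days is scored for sustained cure, or whether that failure is carried forward.

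**The concern.** The second test exists to find infections that return after a first negative. The definition instead measures status at 42-47 days, whatever came before. Under the denominator rule this has two consequences.

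1. **Conversion.** A patient positive at 21-28 days is a failure on the primary outcome, yet becomes a sustained cure if negative at 42-47 days.
2. **Lost specimen.** A patient positive at 21-28 days who returns no second specimen leaves the denominator, although already known not to have a sustained cure.

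A durability rate should not be higher than the cure rate it follows up in the same patients. Here it can be. Positive-to-negative changes can also cancel negative-to-positive changes in the single proportion, so recrudescence could occur and not show. This is the plan's only durability outcome.

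**Working it through.** **Inputs.** Arm sizes (20 or 30) and failure counts (1 to 3) come from Table 2 in Sample size. I take those failures as positives at the 21-28 day test; that is an assumption, because Table 2 concerns precision of cure rates and the plan gives no figure for sustained cure. The 30% loss figure is from the same section. Numbers of conversions and lost specimens are assumed throughout.

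**Step 1: reproduce the plan's figures.** Exact (Clopper-Pearson) 95% intervals match all six rows of Table 2. For example, 17/20 = 85.0% (62.11-96.79) and 27/30 = 90.0% (73.47-97.89). The row shown as 96% is 29/30 = 96.7%; its interval is correct.

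**Step 2: the written rule.** Let N be the arm size, f the positives at 21-28 days, c those later negative and m those with no second specimen. If all first-test negatives are retested and stay negative:

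- cure rate = (N − f)/N
- sustained rate as written = (N − f + c)/(N − m)
- negative at both tests, early positives kept = (N − f)/N

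| N | f | Cure rate | One converts (c=1, m=0) | One lost (c=0, m=1) |
|---|---|---|---|---|
| 20 | 1 | 19/20 = 95.0% | 20/20 = 100% | 19/19 = 100% |
| 20 | 2 | 18/20 = 90.0% | 19/20 = 95.0% | 18/19 = 94.7% |
| 20 | 3 | 17/20 = 85.0% | 18/20 = 90.0% | 17/19 = 89.5% |
| 30 | 3 | 27/30 = 90.0% | 28/30 = 93.3% | 27/29 = 93.1% |

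Each conversion adds 1/20 = 5.0 points in an arm of 20 and 1/30 = 3.3 points in an arm of 30. If every early positive converts or is lost, the written rate is 100%. The overstatement is then f/N: 5, 10 or 15 points for 1, 2 or 3 positives of 20.

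**Step 3: changes that cancel.** N = 20, f = 3, all retested; one positive turns negative and one of the 17 negatives turns positive.

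- As written: (16 + 1)/20 = 85.0%, the same as the cure rate.
- Negative at both tests: 16/20 = 80.0%.
- Change hidden by the summary: 1/17 = 5.9% of early cures (exact 95% CI 0.1-28.7%).

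**Step 4: cases with little or no effect.**

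- Loss unrelated to the first result, at about 30%: 5 of 17 negatives and 1 of 3 positives lost, nobody changing status. As written, 12/14 = 85.7% against 85.0%. The difference is whole-patient rounding (5/17 against 1/3).
- N = 20, one early positive lost, one recrudescence among the other 19: as written, 18/19 = 94.7%, below the cure rate of 95.0%. It still exceeds the 18/20 = 90.0% who are negative at both tests.

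**Step 5: check the replacement estimator.** If early positives are kept but first-test negatives without a second test are dropped, the rate is biased downward. With 3 positives kept and 5 of 17 negatives not retested, 12/15 = 80.0%, although no one retested had relapsed. Multiplying the two stages avoids this:

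- sustained rate = (cure proportion) × (proportion still negative among retested first-test negatives)
- 17/20 × 12/12 = 85.0%, with exact 95% CIs of 62.1-96.8% for 17/20 and 73.5-100% for 12/12 (lower limit 0.025^(1/12) = 0.735)
- worst case, all 5 untested negatives count as relapsed: 12/20 = 60.0%; best case, none does: 17/20 = 85.0%

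In the Step 3 example it gives 17/20 × 16/17 = 16/20 = 80.0%. Because the second factor is at most 1, this estimate cannot exceed the cure rate.

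**The case against.** The intent is largely recoverable. The outcome is named as sustained cure, cure is defined in the same list as a negative 21-28 day test, and the rationale for the second test is relapse after a negative. That is a fair reading of purpose, but an analyst who follows the written definition and denominator would compute something else. Settling the rule now avoids choosing it after results are seen.

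The lost-specimen route needs a missing second test that is related to the first result. Both tests are planned for everyone and reminders are sent, and Step 4 shows essentially no bias when loss is unrelated. This stands. The conversion route, however, needs no missing data.

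The outcome is one descriptive secondary proportion, and a shift of 5 points is small beside an interval of 62.11-96.79%. This also stands and limits the weight of the point.

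A reader might go further and infer that the reported rate will be overstated, that early failures are deliberately excluded, or that they will be retreated and then counted as successes. The documents support none of these. They describe no retreatment and no planned exclusion, and give no rate of positive-to-negative change. The two tests are only 42 − 28 = 14 to 47 − 21 = 26 days apart. The 5, 10 and 15 points in Step 2 are extremes for 1 to 3 early positives, not expectations.

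**Conclusion.** The point holds as a defect in a stated scoring rule. As written, the sustained rate can exceed the cure rate and can mask recrudescence. One affected patient shifts it by about 5 points in an arm of 20 and about 3 points in an arm of 30, given Table 2's failure counts and all other patients retested and still negative. How often this would happen is unknown, and the effect may be zero. A patient negative first and positive second who is retested is already scored correctly as not sustained. The primary outcome, futility rule and sample size are unaffected, and no between-regimen comparison of sustained cure is specified. The change is worth making because it is cheap and aligns the outcome with its stated purpose. Confidence is high in the reading of the text; no claim is made about the practical size.

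**What to change.** 1. In Outcomes, define sustained microbiologic cure as a negative Aptima test at both 21-28 and 42-47 days. Score any 21-28 day positive as not sustained, and keep that patient in the denominator whether or not a second specimen is returned.
2. In Data analysis, give the point estimate as the 21-28 day cure proportion times the proportion still negative among retested first-test negatives. Report each component with its exact 95% CI. State the assumption that first-test negatives who were not retested relapse at the same rate as those who were.
3. Add best- and worst-case bounds for first-test negatives without a second result, as a sensitivity analysis.
4. Cross-tabulate the two results, including missing, so that changes in each direction are visible.

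**Cost.** A few sentences and one small table, with no new specimens or survey items. The sustained-cure figure may be slightly less favourable, and the bounds will be wide if many second tests are missing.

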# **Criteria for futility**

Given the absence of alternative therapies for *M. genitalium* treatment failures, even modest efficacy of 60% would be useful for some patients. Therefore, futility will be defined as <5% probability that true efficacy is 60% (or higher), given the number of treatment failures that occur in the first 10 patients. The probability of observing three or fewer cures (e.g., at least 7 treatment failures) in the first 10 patients if the true efficacy is 60% is 5%. Therefore, if three or fewer of the first ten patients in either arm experience microbiologic cure, we would declare futility for that regimen.

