# Study Design

We propose to provide compassionate access to lefamulin and estimate the efficacy of lefamulin in treating antibiotic resistant MG through a coordinating center at the University of Washington (UW). We will enroll a total of 40 symptomatic patients with MG infections who have experienced treatment failure after moxifloxacin and/or other second or third line antimicrobials

or in whom moxifloxacin is contraindicated. Patients will be followed for 42 or 56 days, depending on the regimen they receive.

There is an increasing global trend to pre-treat MG infections with doxycycline to reduce organism load. There have also been several initial reports of treatment failure after a 7-day regimen of lefamulin alone, but successes after a regimen in which patients were pre-treated with doxycycline in the companion study in Melbourne, Australia. Therefore, we propose to also determine if pre-treatment with doxycycline is necessary. To simultaneously assess the efficacy of lefamulin alone (600mg orally twice daily for 7 days), and a regimen incorporating pre-treatment with doxycycline 100mg orally twice daily for 7 days followed by lefamulin 600mg orally twice daily for 7 days), we will randomize the first 20 patients to either Regimen A (lefamulin alone) or Regimen B (pretreatment with doxycycline followed by lefamulin) in a 1:1 ratio.

An interim analysis will be performed after the first 20 patients are enrolled to assess the efficacy of each of these two regimens for futility. Based on the results of this interim analysis, we will make one of three possible decisions:

- If neither of the regimens meet criteria for futility, we will continue randomizing patients to one of the two regimens until we have reached our target sample size of 40 patients (20 randomized per arm).
- If one of the regimens meets criteria for futility but the other regimen does not, we will drop the regimen that met futility criteria and continue to administer the other regimen to the remaining 20 patients for a total of 30 randomized patients in the retained regimen.
- If both regimens meet criteria for futility, we will halt the study and reassess the possibility of using alternative dosing regimens.

Criteria for futility are outlined in the section on sample size on p. 6.

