# Timeline and publication

We estimate it will take one calendar year to enroll and follow 40 patients. Data analysis and preparation of a final report for Nabriva and a peer-reviewed publication will be completed within 12 weeks of the completion of the last follow-up visit of the final participant.

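### The futility rule does not say how a missing test of cure counts, and its two wordings (3 or fewer cures, 7 or more failures) part company once a test is missing

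*Combined protocol and SAP*

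**What the plan says.** The combined protocol and SAP sets the rule under Criteria for futility. The definition is that "futility will be defined as <5% probability that true efficacy is 60% (or higher"), given the failures seen in the first ten patients. The supporting calculation puts the probability of "three or fewer cures (e.g., at least 7 treatment failures) in the first 10 patients if the true efficacy is 60% is 5" per cent. The operating rule is then a count: "if three or fewer of the first ten patients in either arm experience microbiologic cure, we would declare futility for that regimen".

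Four other sections bear on how that count is made:

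- Study Design, on timing: "An interim analysis will be performed after the first 20 patients are enrolled".
- Outcomes, on the endpoint: "Microbiologic cure defined as a negative Aptima MG test", taken 21-28 days after lefamulin is completed.
- Sample size, on missing data: "Assuming loss to follow-up of up to 30" per cent. This inflates a target of 30 patients with complete data on tests of cure, adherence and adverse events.
- Data analysis, on the reported proportions: "the denominator will be the total number of patients for whom we have complete outcome data for the outcome of interest". It does not mention the futility rule and gives no cutoff for fewer than ten results.

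**The concern.** Cure needs an observed negative test, specimens are self-collected and mailed, and the plan itself allows for loss, so some of the first ten patients in an arm may well have no result at the interim. The plan does not say whether such a patient is not cured, not a failure, or left out.

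The futility section offers two descriptions of the stopping event that are interchangeable only when all ten results are in. Suppose an arm has 3 cures, 5 failures and 2 missing tests. By the count of cures it is futile (3 or fewer). By the count of failures it is not (5, short of 7). As a proportion of those tested it has 3/8 = 37.5% cured.

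This rule alone decides whether a regimen is dropped or the study halts. The same section regards 60% efficacy as worth having for these patients. If the choice is made after the interim data are seen, the same data can support either decision.

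**Working it through.** **Inputs.** Cutoff 3 of 10 and efficacy 60% (Criteria for futility); loss L up to 30% (Sample size). L = 10% and 20% are assumed for illustration. Loss is taken as independent of cure. A 30%-effective arm is used as an example of one that the rule should drop.

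**1. The plan's own figure.** With ten results, P(X ≤ 3 | n = 10, p = 0.6) = 0.0001 + 0.0016 + 0.0106 + 0.0425 = 0.0548. The printed 5% is reproduced after rounding. As a binomial tail it is not below 5%.

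**2. Three readings when tests are missing.**

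- *Missing counted as not cured.* Cures follow Bin(10, 0.6(1 − L)), and the arm is dropped if X ≤ 3. At L = 30% the cure parameter is 0.42.
- *Seven observed failures required.* Failures follow Bin(10, 0.4(1 − L)), and the arm is dropped if there are 7 or more. At L = 30% the failure parameter is 0.28.
- *30% or fewer cured among those tested.* The number tested m follows Bin(10, 1 − L), and P(X ≤ floor(0.3m) | m, 0.6) is averaged over m. No section states this cutoff; it is a conversion of 3/10 to a proportion.

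| Chance of dropping a 60%-effective arm | 10% loss | 20% loss | 30% loss |
|---|---|---|---|
| Missing = not cured | 11.4% | 20.7% | 33.3% |
| Seven observed failures | 3.1% | 1.6% | 0.7% |
| 30% or fewer of those tested | 4.5% | 5.4% | 6.65% |

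The last row is an average. By number tested it is 5.5% (10), 2.5% (9), 5.0% (8) and 9.6% (7).

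**3. The other side of the error.** With ten results, a 30%-effective arm is dropped with probability P(X ≤ 3 | 10, 0.3) = 65%. If seven observed failures are required and loss is 30%, failures follow Bin(10, 0.7 × 0.7 = 0.49) and that arm is dropped only 16% of the time. The rule then does little.

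**4. Both arms.** Let a be the chance of dropping one 60%-effective arm. With two such arms, at least one is dropped with probability 1 − (1 − a)² and the study halts with probability a². With full results (a = 0.0548) these are 10.7% and 0.3%. With missing counted as not cured and 30% loss (a = 0.3335) they are 56% and 11%.

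**5. Pending tests, if the interim were run at the 20th enrolment.** Timeline and publication says "We estimate it will take one calendar year to enroll and follow 40 patients". That is 40/52 = 0.77 patients per week, or 40/43.3 = 0.92 after deducting 61 days (14 of treatment, 47 of follow-up) for the last patient. A result falls due 28-35 days after the first dose in Regimen A and 35-42 in Regimen B, so 4 to 6 weeks. Hence 0.77 × 4 = 3.1 to 0.92 × 6 = 5.5 earlier patients, plus the 20th, are still waiting: about 2 to 3 per arm.

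**The case against.** The strongest reply is that the error need not be inflated at all. The futility section conditions on the number of failures, and an untested patient is not an observed failure. On that reading missing tests make futility harder to declare. This stands. A reader might infer that the rule as written drops a useful regimen a third of the time, but the documents do not support that as a finding: they never say that a missing test counts as not cured. Also, 30% is an upper limit set for complete data on several outcomes, so loss of the 21-28 day test alone may be smaller.

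A second reply is that the Data analysis section settles the matter through its complete-case denominator. It fixes a denominator for reported proportions and no cutoff. Keeping 3 or fewer cures among those tested still gives 11.4% to 33.3%. The 4.5% to 6.65% range needs a 30% cutoff that the plan does not contain.

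A third is that the team would obviously wait for results, the 20 enrolled patients being the cohort and not the date. That is a fair reading, and it makes the pending count conditional. Waiting does not resolve lost tests, however, and the plan does not state it.

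Nor should one infer that an error near 5% is possible only with ten results. With 8 tested and a cutoff of 2 cures it is 4.98%.

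**Conclusion.** The gap holds. The rule is specified for ten results per arm, the plan expects that some may be missing, and its two descriptions of the stopping event then move the error in opposite directions. At the plan's ceiling of 30% loss, the chance of dropping a 60%-effective arm is 33.3% or 0.7% depending on which description is applied, against the stated 5%. At an assumed 10% loss it is 11.4% or 3.1%. These figures rest on loss independent of cure and ten patients randomised per arm. The direction of the error is undetermined; what is established is that the rule does not fix it.

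The 5.48% against a criterion of below 5% is a minor point of wording. The criterion could also be read as a posterior probability: with a flat prior (an assumption, as no prior is given), 3 cures of 10 gives 2.9% and meets it.

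This should be fixed before any interim data are seen.

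**What to change.** In Study Design and Criteria for futility:

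- Apply 3 or fewer cures of 10 to the first ten patients per arm with an evaluable 21-28 day Aptima result.
- State that a lost or pending test counts as neither cure nor failure.
- Restate the criterion as a 5.5% probability of 3 or fewer cures if true efficacy is 60%.
- State whether enrolment pauses while results are awaited.

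**Cost.** The wording change is small, but the interim comes later. On average both arms reach ten results after about 11.7 randomised per arm at 10% loss (2 × 11.7 − 20, about 3 extra patients) or 15.6 per arm at 30% (about 11 extra). If one arm is then dropped, the retained arm ends near 40 − 11.7 = 28 or 40 − 15.6 = 24, not the planned 30. If enrolment does not pause, about 4 to 5 more patients are randomised while the last results come in, and the retained arm ends near 26 or 22. At 30% loss there is about a 3% chance that an arm has not reached ten results by 20 randomised.

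**Alternative.** If the interim must use only the first 20 patients, wait for their 28-day windows to close. Fix one cutoff for fewer than ten results in advance, for example 30% or fewer cured of those tested, and state its error (4.5% to 6.65% on average over 10% to 30% loss, but 9.6% with seven tested). This needs no extra patients. At 30% loss it drops a 30%-effective arm 54% of the time, against 65% with ten results.
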